	Exclusion criteria: Patients with current urinary retention, post void residual urine > 250ml, active urinary tract infection at time of treatment, previous BPH procedure, urethral conditions that may prevent insertion and delivery of device system into bladder, previous		

Version no.6.0 of 31/01/2023 pelvic surgery or irradiation, history of neurogenic or atonic bladder, biopsy of the prostate within the past 6 weeks, life expectancy estimated to be less than 1 year, history of prostate or bladder cancer, PSA>10ng/ml unless prostate biopsy is negative, person guardianship or curatorship will not be included in the cohorts. Patients intending to move abroad within 1 year after inclusion will not be included either. Person participating to another interventional study on benign prostatic hyperplasia during the study. Patients of the PUL and TURP/LASER cohorts will be identified in the SNDS through their NIR national identifier (if possible) or using a probabilistic linkage with age, hospital identifier (FINESS), date of hospitalization for the procedure and ICD-10 discharge diagnosis. Only patients with a 2-year history before the procedure and a 3-year follow-up after the procedure will be analysed. The SNDS cohort: Inclusion criteria: male patients affiliated to a French health

insurance system aged over 50 years who experienced a TURP/Laser surgery in first line of treatment for a symptomatic BPH in the same period as patients of the PUL and TURP/LASER cohorts.

Exclusion criteria: Patients hospitalized in one of the 7 investigational centers and patients with a previous BPH procedure, a previous pelvic surgery or irradiation, history of prostate or bladder cancer within the 2 previous years, a biopsy of the prostate within the past 6 weeks, or with a short life expectancy will not be included in the

Matching criteria: A total of 5 patients will be matched to 1 patient of the PUL cohort for each procedure (TURP, HLE, GLV) according to age, date of the procedure (same month) and a high dimensional disease risk score (hDRS) based on the one-year SNDS information before the transurethral procedure.

RESEARCH PROCEDURES/ **STRATEGIES**

OUTCOMES

The studied procedures are:

- The experimental procedure: PUL, consisting in transurethral placement of permanent UroLift implants into the lobes of the prostate. The intent of PUL procedure is to retract the lobes of the prostate in order to reduce prostatic obstruction.

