5.1.2. EXCLUSION CRITERIA

- Current urinary retention
- Post void residual urine > 250ml
- Active urinary tract infection at time of treatment

- Previous BPH procedure
- Urethral conditions that may prevent insertion and delivery of device system into bladder (i.e. urethral strictures, meatal stenosis, bladder neck contracture)
- Previous pelvic surgery or irradiation
- History of neurogenic or atonic bladder
- Biopsy of the prostate within the past 6 weeks
- Life expectancy estimated to be less than 1 year
- History of prostate or bladder cancer
- PSA>10ng/ml unless prostate biopsy is negative
- Person intending to move abroad within 1 year after inclusion
- Person placed under guardianship or curatorship
- Person participating to another interventional study on benign prostatic hyperplasia during the study

Patients of the PUL and TURP/LASER cohorts will be identified in the SNDS through their NIR national identifier (if possible) or using a probabilistic linkage with age, hospital identifier (FINESS), date of hospitalization for the procedure and ICD-10 discharge diagnosis. Only patients with a 2-year history before the procedure and a 3-year follow-up after the procedure will be analyzed.

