5.2. SNDS COHORT

5.2.1. INCLUSION CRITERIA

- Male Gender
- Patients hospitalized for transurethral surgery for first line treatment of symptomatic BPH in the same period as patients of the PUL and TURP/LASER cohorts (i.e. hospitalisation with the main diagnosis ICD-10 code N40 and the surgical procedure codes JGFE023 for TURP, JGFE365 for HLE and JGNE171 for GLV);
- Affiliated to a French health insurance system

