5.2.2. EXCLUSION CRITERIA

- Patients hospitalized in one of the 7 investigational centers
- Patients with a previous BPH procedure previous pelvic surgery or irradiation, history of prostate or bladder cancer (2-year database history and/or Long term disease registration)
- Patients with biopsy of the prostate within the past 6 weeks
- Patients with short life expectancy based on a Charlson Comorbidity Index ≥ 10 (this threshold reflects the presence of metastasis or an equivalent health condition) (cf. Bannay and al., 2015).

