5.2.3. MATCHING CRITERIA

A total of 5 patients will be matched to 1 patient of the PUL cohort for each procedure (TURP, HLE, GLV) according to age, date of the procedure (same month) and a high dimensional disease risk score (hDRS) based on the one-year SNDS information before the surgical procedure. The Disease Risk Score (DRS) estimates the probability of complications occurrence in the absence of the surgery of interest (PUL). DRS will be computed from a multivariable logistic regression model using a large set of variables collected during the one-year period among the SNDS cohort.

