6. THE SNDS

The nationwide healthcare insurance system database, the SNDS (*Système National des Données de Santé*) contains individual anonymous information on all reimbursed outpatient claims (SNIIRAM) linked to the national hospital-discharge summaries database system (PMSI) and the national death registry (CépiDC), using a unique national pseudonymised identifier. It currently includes 99% of the French population, more than 66.6 million persons from birth (or immigration) to death (or emigration), even if a subject changes occupation or retires. Both EGB and SNDS contains individual pseudonymised information on (TUPPIN 2010, BEZIN 2017):

- General characteristics: gender, year of birth, affiliation scheme, area of residence;
- Date of death for those concerned and cause of death with a lag of 2-3 years;
- Long-Term disease registration (LTD ALD: "Affection longue durée" in French) and associated ICD10 codes, including most of chronic diseases with long term and/or expensive treatment. Registration with a LTD is obtained at the request of a patient's practitioner and must be validated by the health insurance system physician. Once registered, patients receive full (i.e. 100%) reimbursement for expenditure related to the LTD, as defined by the health authorities. The LTD information is specific for the diagnosis (very low risk of false positives), but not sensitive because not all patients with the disease ask to benefit from a LTD;
- Outpatient reimbursed healthcare expenditures: visits, medical procedures, nursing acts, physiotherapy, medical imageries, lab tests, drugs with dosage and number of boxes dispensed, medical devices, transports, sick leaves... with prescriber and professional caregiver information (medical or paramedical specialty, private/public practice), dates (prescription and dispensing), and codes (e.g. ATC codes for drugs, LPP codes for medical devices), but not the medical indication nor result;
- Hospital-discharge summaries from the PMSI: ICD10 diagnosis codes (primary, related and associated diagnosis) for all private and public medical, obstetric and surgery's hospitalizations, with the date and duration of the hospital stay, medical procedures, and cost coding system, as well as most of very costly drugs. The hospital discharge summary includes the medical unit summaries when the patient is hospitalized successively in several medical units.

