9.8. SNDS ASSESSMENTS

For each patient identified in the SNDS cohort, the following settings will be defined:

- Inclusion date: date of the surgical procedure completion
- **Look-back period:** 2 years preceding the inclusion date;
- **Follow-up period:** 3 years following the inclusion date.

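### In the complementary PUL versus SNDS comparison, earlier BPH or pelvic surgery excludes PUL patients without time limit but is ascertained over only two years, plus long-term-disease registration, in the SNDS comparators

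*Protocol*

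**What the plan says.** For both field cohorts (PUL and TURP/laser), Protocol section 5.1.2 lists "Previous BPH procedure" as an exclusion. It also lists previous pelvic surgery or irradiation. Neither carries a time window.

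For the SNDS cohort, section 5.2.2 names the same exclusions together with prostate or bladder cancer, followed by a bracket on how they are found: "2-year database history and/or Long term disease registration". The synopsis attaches the two years to the end of its list: "history of prostate or bladder cancer within the 2 previous years". Section 9.8 sets the look-back for each SNDS patient at "2 years preceding the inclusion date".

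Three further passages bear on whether an older operation could be seen in another way:

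- Section 5.2.1 requires first-line treatment and defines it operationally by the index stay: "hospitalisation with the main diagnosis ICD-10 code N40 and the surgical procedure codes JGFE023 for TURP, JGFE365 for HLE and JGNE171 for GLV".
- Section 5.2.3 matches on age, month of procedure and a high dimensional disease risk score "based on the one-year SNDS information before the surgical procedure".
- Section 6 describes long-term-disease registration as "including most of chronic diseases with long term and/or expensive treatment", and calls it specific but not sensitive.

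Section 1.3 presents the SNDS match as complementary to the field comparison. It says that the matched comparators share the baseline characteristics of the PUL patients, and that matching and adjustment will make up for the lack of randomisation.

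**The concern.** The same exclusion is applied over two different windows. A PUL patient operated on for BPH ten years ago is ineligible. An SNDS patient with the same history passes the two-year screen unless something else reveals the operation, and he then counts as a first-line comparator.

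Section 1.1.2.1 itself says that recurrent symptoms may lead to a second operation, so such men can be expected to exist. The outcomes of the SNDS comparison include retreatment and hospitalisation for retention or stricture at 1 and 3 years (section 3.2), and earlier surgery could plausibly affect these. If the comparators contain repeat operations and the PUL cohort does not, part of any difference may reflect surgical history and not the procedure. The results are meant to support reimbursement, so the claim of comparability should match what the data rule can deliver.

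**Working it through.** **Step 1. Can any rule in the protocol identify an operation more than two years old in an SNDS patient?**

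| Rule | Section | Sees an older BPH operation? |
|---|---|---|
| Two-year database history | 5.2.2, 9.8 | No, outside the window |
| Long-term-disease registration | 5.2.2, 6 | Not described as doing so; it registers chronic diseases, so it may help with cancer history |
| N40 plus index procedure code | 5.2.1 | No; describes the index stay and does not separate a first operation from a repeat |
| Disease risk score | 5.2.3, 11.2.2 | Not directly; its one-year window lies inside the two-year window |
| Age and month of procedure | 5.2.3 | No |

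The bracket in 5.2.2 could be read as applying to cancer history only, as the synopsis wording suggests. Section 9.8 still fixes the look-back at two years for every SNDS patient, so the result does not depend on that reading.

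**Step 2. Which analyses are affected?** Sections 4.2 and 11.2.3 base the 4-month cost per avoided complication and the 12-month cost per QALY on PUL versus the TURP/laser cohort. Both fall under section 5.1.2. The cost per QALY takes claims from the SNDS, but for those two cohorts. Neither ratio involves the SNDS cohort. The TURP/laser cohort also has 3-year SNDS follow-up (section 4.1), so the longer-term outcomes have one comparison without this mismatch.

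**Step 3. The plan's own figures.** 80 PUL patients x 5 matches = 400 per procedure, and 400 x 3 = 1200, as in section 11.1. The 95% half-width is 1.96 x sqrt(p(1-p)/n). At n = 400 this gives 2.94% for p = 10% and 4.90% for p = 50%, which reproduces the stated 3% to 5%. At n = 80 and p = 10% it gives 6.57%, the stated 7%.

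**Step 4. Possible size.** The protocol gives neither the share q of SNDS comparators whose index operation is a repeat after more than two years, nor their risk ratio RR against first operations. Both are assumptions here. The base rate b = 10% is also illustrative; it is the lower end of the range for which section 11.1 states precision.

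Observed rate = b(1-q) + b x RR x q, so shift = b x q x (RR-1).

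| q (men per 400) | RR 0.75 | RR 1.25 | RR 1.5 | RR 2 |
|---|---|---|---|---|
| 2% (8) | -0.05 | +0.05 | +0.10 | +0.20 |
| 5% (20) | -0.125 | +0.125 | +0.25 | +0.50 |
| 10% (40) | -0.25 | +0.25 | +0.50 | +1.00 |

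Shifts are in percentage points. At the extremes, 0.10 x 0.10 x (0.75-1) = -0.0025 and 0.10 x 0.10 x (2-1) = +0.010. The shift is proportional to b: at a 20% base rate the range becomes -0.5 to +2.0 points. The number of controls n does not appear in the formula, so a larger matched cohort leaves the shift where it is.

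**The case against.** The strongest reply is that this touches a secondary comparison and is small against sampling error. Both parts are fair. The primary result and the cost per QALY are untouched, and the largest shift in the table, 1.0 point, is below the 2.94-point half-width for 400 comparators and well below the 6.57 points for 80 PUL patients. What remains is that the shift is systematic, so it does not average out and the confidence interval does not reflect it.

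It can also be said that the risk score draws on a large set of variables from the year before surgery, so recent correlates of an old operation may be partly balanced. That is possible. The score cannot see the operation itself, and the protocol gives no basis for saying how much of the imbalance it would remove.

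A reader might be tempted to stronger statements that the protocol does not support:

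- *That the two years are purely a choice because the database covers a lifetime.* Section 6 says the SNDS includes "more than 66.6 million persons from birth (or immigration) to death (or emigration"). That describes who is covered. No section says how many years of claims or hospital records can be extracted, and access needs authorisation.
- *That the 13.6% surgical retreatment in section 1.1.2.2 gives the share of repeat operations.* It is a rate after PUL in a North American and Australian trial, and section 1.6 says the device has been little used in France. It is also the share of treated men later retreated, not the share of index operations that are repeats. It cannot stand in for q.
- *That the mismatch favours PUL.* This is plausible if repeat operations carry more risk, but the protocol gives no risk ratio, and the sign reverses if RR is below 1.

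**Conclusion.** The mismatch is in the current text and no other section repairs it. Followed as written, the plan can admit men with an older BPH operation, pelvic surgery or irradiation to an SNDS cohort labelled first line, while such men are barred from the PUL cohort. That they are present is a reasonable inference, not a documented count.

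The consequence is limited to the PUL versus SNDS comparison. On the assumptions stated (q from 2% to 10%, RR from 0.75 to 2, base rate 10%) the comparator rate would move by about -0.25 to +1.0 percentage points. The protocol establishes neither direction nor size. The case for acting is that the rule is fixed in the eligibility section and determines what is extracted, that correction is cheap before extraction, and that years not requested cannot be recovered by a later analysis of the same extract.

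**What to change.** In section 5.2.2, and in the Data Extraction Plan before the first extraction (planned for Q4 2025 in the synopsis), screen codes for previous BPH procedure, pelvic surgery and irradiation over the longest SNDS/PMSI history that can be authorised. State that window. Keep 2 years for the other variables, and amend section 9.8 so that its look-back allows the exception.

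If a longer window cannot be obtained, describe the SNDS cohort as having no BPH procedure in the previous 2 years instead of as first line, and limit the statement in section 1.3 about shared baseline characteristics accordingly.

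The cost is a wider data authorisation for a short list of codes and slightly fewer eligible comparators. The fallback costs only wording.

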5.2.3. MATCHING CRITERIA

A total of 5 patients will be matched to 1 patient of the PUL cohort for each procedure (TURP, HLE, GLV) according to age, date of the procedure (same month) and a high dimensional disease risk score (hDRS) based on the one-year SNDS information before the surgical procedure. The Disease Risk Score (DRS) estimates the probability of complications occurrence in the absence of the surgery of interest (PUL). DRS will be computed from a multivariable logistic regression model using a large set of variables collected during the one-year period among the SNDS cohort.

5.3. FEASIBILITY AND RECRUITMENT PROCEDURES

Investigational centers have been chosen based on their large experience in conducting clinical trials in the field of BPH.

All sub-investigators also have been chosen based on their significant clinical activity in the field of BPH (at least 80 trans-urethral procedures a year).

Recruitment is planned to last 24 months and will be dispatched as follows between participating centers:

Center	Cohort PUL	Cohort TURP/Laser		
Bordeaux	12	12		

Paris Cochin	12	12
Lille	11	11
Tours	11	11
Montpellier	11	11
Lyon	11	11
Quint Fonsegrives	12	12
Total	80	80

In order to ensure quick and equal recruitment in both groups the following measures will be applied:

- Recruitment will be competitive after the first 6 months of inclusion;
- Recruitment will be stopped if not equally dispatched between groups (if a participating center does not recruit equally in both groups recruitment in the first group will be stopped until patients have been recruited in the other group). A difference of 3 cases between groups will be tolerated.

6. THE SNDS

The nationwide healthcare insurance system database, the SNDS (*Système National des Données de Santé*) contains individual anonymous information on all reimbursed outpatient claims (SNIIRAM) linked to the national hospital-discharge summaries database system (PMSI) and the national death registry (CépiDC), using a unique national pseudonymised identifier. It currently includes 99% of the French population, more than 66.6 million persons from birth (or immigration) to death (or emigration), even if a subject changes occupation or retires. Both EGB and SNDS contains individual pseudonymised information on (TUPPIN 2010, BEZIN 2017):

- General characteristics: gender, year of birth, affiliation scheme, area of residence;
- Date of death for those concerned and cause of death with a lag of 2-3 years;
- Long-Term disease registration (LTD ALD: "Affection longue durée" in French) and associated ICD10 codes, including most of chronic diseases with long term and/or expensive treatment. Registration with a LTD is obtained at the request of a patient's practitioner and must be validated by the health insurance system physician. Once registered, patients receive full (i.e. 100%) reimbursement for expenditure related to the LTD, as defined by the health authorities. The LTD information is specific for the diagnosis (very low risk of false positives), but not sensitive because not all patients with the disease ask to benefit from a LTD;
- Outpatient reimbursed healthcare expenditures: visits, medical procedures, nursing acts, physiotherapy, medical imageries, lab tests, drugs with dosage and number of boxes dispensed, medical devices, transports, sick leaves... with prescriber and professional caregiver information (medical or paramedical specialty, private/public practice), dates (prescription and dispensing), and codes (e.g. ATC codes for drugs, LPP codes for medical devices), but not the medical indication nor result;
- Hospital-discharge summaries from the PMSI: ICD10 diagnosis codes (primary, related and associated diagnosis) for all private and public medical, obstetric and surgery's hospitalizations, with the date and duration of the hospital stay, medical procedures, and cost coding system, as well as most of very costly drugs. The hospital discharge summary includes the medical unit summaries when the patient is hospitalized successively in several medical units.
 - Primary diagnosis is the health problem that motivated the admission in the hospital. It is determined at
 hospital discharge. For patients hospitalized successively in several medical units, the primary diagnosis
 of the hospitalization, as well as for all medical unit primary diagnosis, are generally taken into account to
 define the occurrence of an outcome in a pharmacoepidemiology study.
 - A related diagnosis can exist only if the primary diagnosis is a care procedure with a code Z of the ICD10 classification (e.g. chemotherapy session) for a chronic or LTD disease. It indicates the pathology at the origin of the care procedure.
 - Associated diagnoses are specified mainly if they represent specific healthcare resources. They are mainly
 underlying chronic diseases. Associated diagnoses can be used to define chronic diseases but are
 generally not taken into account to define the occurrence of an outcome in a pharmacoepidemiology study
 (many being false positives for the studied outcome).

Access to SNDS is regulated and needs approval from the National Institute of Health Data (*Institut National des Données de Santé* - INDS), the committee in health data research (*Comité d'Expertise pour les Recherches, les Etudes et les Evaluations dans le domaine de la Santé* - CEREES), and the French data protection commission (*Commission Nationale de l'Informatique et des Libertés* - CNIL).

7. STUDY INTERVENTION

7.1. INVESTIGATIONAL PROCEDURE: PROSTATIC URETHRAL LIFT

Prostatic urethral lift (PUL) consists in transurethral placement of permanent UroLift implants in both lateral lobes of the prostate. PUL intends to retract the lateral lobes of the prostate in order to reduce prostatic obstruction.

Based on clinical studies, between four to six implants are needed to treat one patient (based on the results of the Lift study) but the number of implants needed to treat each patient will be left at the discretion of the surgeon inside clinical study.

All procedures will be performed under local anaesthesia. Nitrous oxide inhalation use will be permitted, but we won't use oral or intravenous sedation.

In order to avoid complications related with the learning curve a proper training of the surgeons will be organized upfront starting of clinical study: a minimum of 15 cases performed under local anaesthesia in a day-care surgical unit will be required before entering clinical study.

One surgeon per investigating center will be trained and qualified to include patients in the PUL group.

Cases with obstructive median lobe of the prostate will not be excluded as was done in the precedent PUL studies (LIFT and BPH6), but will be treated only by advanced users as in the recently published MedLift study.

7.2. COMPARATIVE PROCEDURE: CLASSIC PROSTATIC ENDOSCOPIC SURGERY

Patients included in the TURP/Laser cohort will be treated following the habits of each investigating center (TURP, laser enucleation or laser vaporization will be allowed).

One surgeon per investigating center will be allowed to include patients in the trans-urethral surgery cohort. This surgeon will be different from the one including in the PUL group (if not possible, it can be exceptionally the same surgeon).

In order to avoid complications related with the learning curve this surgeon will have to be sufficiently experienced with transurethral surgery (experience of more than 100 trans-urethral surgical treatment will be required for entering this clinical study).

